##### *Medical Records Review*

Baseline information, operative information, and outcomes will be determined via retrospective review of medical records. Data obtained via medical record review will include demographic information (age, gender, ethnicity), baseline clinical information (medical co-morbidities, medications, history of underlying cause of peripheral artery disease, etc.) data on the operation (date of operation/procedure, discharge date, surgeons name, anatomical site, campus where the surgery was performed, type of anesthesia, intraoperative blood pressures, estimated blood loss, intraoperative complications, etc.), results of standard-of-care exams.

##### *Data Processing Procedure*

The data collectors will complete the data forms and review all items for accuracy. All information will be entered into an electronic excel database created for the study.

##### *Statistical Analysis*

A retrospective chart review will be conducted on a maximum of 500 patients. Analyzing data from 500 patients will provide a robust baseline to conduct a study of differences, similarities, and trends among the patients. All information will be entered into an electronic excel database created for the study and analyzed in STATA statistical program. All subjects meeting eligibility criteria will be enrolled.

The data will be abstracted from Houston Methodist Hospital electronic medical records, DigiView and from the MCVSA office charts by the PI and trained members of his research staff. The required information will be transferred from electronic medical records by the research staff to the study specific electronic Excel data collection forms.

**PROTOCOL TITLE: *Ultrasound Evaluation for Baxter VASCU-GUARD Vascular Patches Post-Endarterectomy and Complications Assessment***

Permission to review medical records will be obtained from the Houston Methodist Hospital Research Institute (TMHRI) Human Subjects Committee via a HIPAA Waiver of Authorization and Waiver of Consent.

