## 2. Purpose of the Study / Objectives

**PROTOCOL TITLE: *Ultrasound Evaluation for Baxter VASCU-GUARD Vascular Patches Post-Endarterectomy and Complications Assessment***

Primarily focusing on the implementation of VASCU-GUARD vascular patches in carotid endarterectomies (CEA), the study aims to identify VASCU-GUARD patches with old (before January 2023) and new (after January 2023) packaging and compare the results of standard-of-care exams between the two groups.

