#### 4. Study Design

This study is a retrospective chart review. The data is collected from January the 1st 2022 till April the 30th 2024.

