## 10. Study Population

The study population is patients undergoing carotid endarterectomy (CEA) with the use of Baxter VASCU-GUARD vascular patches in all campuses of the Houston Methodist Hospital.

Inclusion criteria:

- Patients aged 18 years and above.
- Patients undergoing carotid endarterectomy with the use of VASCU-GUARD vascular patches.
- Follow-up ultrasound assessment available.

Exclusion criteria:

- No postoperative ultrasound assessment is available.

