## 11. Screening and Recruitment SR

Subjects will be retrospectively identified through retrospective review of medical records.

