### **Waiver of HIPAA Authorization for Research**

Complete this section if you will access identifiable health information in a patient's electronic health record or other record held by Houston Methodist Hospital and you are not obtaining a signed authorization from the patient. This waiver can apply to health information accessed to identify potential research participants or for research involving retrospective chart reviews.

1. Purpose of the Waiver:

- Chart review study – collecting retrospective clinically available data that will not have bearing on clinical outcomes.
- Partial waiver of authorization to identify, prescreen and contact potential participants.
- Alteration of the requirements for a HIPAA Authorization to remove the signature. \*
- Other Please explain Retrospective Study – clinically available data only

***\* Note if the IRB waives the signature requirement, the participant must receive a copy of the HIPAA authorization language.***

2. Provide protocol-specific responses to the following items that describe why the waiver is being requested for the use of PHI in this research.

a. The IRB must find that the use/disclosure of protected health information (PHI) involves no more than minimal risk to the privacy of individuals. Please select the safeguards your team will use to meet this requirement.

- Electronic safeguards, such as password protection, data encryption, and institution firewall, will be used to protect PHI
- Physical safeguards, such as locked cabinets, locked filing room, secure, locked office area, will be used to protect PHI
- The study team will record only anonymous data or coded data that are linked to the participants' identity through a file that is separate from the data.
- Administrative safeguards such as policies and procedures, staff education on the HIPAA Privacy Rule.

Other: \_\_\_\_\_

c. Describe why the research cannot practically be conducted without the waiver or alteration of patient authorization to use PHI in research

- Access to and use of PHI is necessary to obtain information of potential subjects.
- The number of screen failures is anticipated to be high for this research and access to

**PROTOCOL TITLE: *Ultrasound Evaluation for Baxter VASCU-GUARD Vascular Patches Post-Endarterectomy and Complications Assessment***

the PHI to confirm potential study eligibility will prevent unnecessary contact with potential participants.

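### Does a ceiling of 500 patients contradict the statement that every eligible patient is enrolled?

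*Protocol*

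**What the plan says.** The size statements stand together in Protocol section 4, under Statistical Analysis:

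- a ceiling: "A retrospective chart review will be conducted on a maximum of 500 patients";
- a reason for that number: "Analyzing data from 500 patients will provide a robust baseline to conduct a study of differences, similarities, and trends among the patients";
- an inclusion rule: "All subjects meeting eligibility criteria will be enrolled".

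Other sections bear on how many patients there will be and how they are grouped. Section 4 sets the data window as 1 January 2022 to 30 April 2024. Section 2 forms the comparison groups by calendar time: "the study aims to identify VASCU-GUARD patches with old (before January 2023) and new (after January 2023) packaging". Section 10 covers all campuses but excludes a patient when "No postoperative ultrasound assessment is available". Section 11 says that "Subjects will be retrospectively identified through retrospective review of medical records". The HIPAA waiver in section 18 expects many screen failures: "The number of screen failures is anticipated to be high for this research and access to". No section gives a surgical volume or an expected number of eligible patients.

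**The concern.** Taken literally, the statements set the number of patients as at most 500, as 500, and as however many qualify. A reader could ask which of these governs.

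Two consequences seemed possible. If fewer than 500 qualify, the only argument offered for the size describes a number that will not be analysed. If more than 500 qualify, the ceiling and the inclusion rule cannot both be followed, and nothing says who is left out.

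The second would matter more here than in most chart reviews. The groups are defined by surgery date, so the order in which a binding ceiling is filled would set the group sizes and the calendar periods represented. Patients are also found in medical records that already hold their outcomes, so a late choice of whom to omit could be made with results in view.

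**Working it through.** **Consistency.** Let E be the number eligible and n the number included.

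- Ceiling: n ≤ 500.
- Inclusion rule: n = E.
- Rationale, if read as a rule: n = 500.

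Trying every E from 0 to 2000, all three hold only at E = 500. The ceiling and the inclusion rule alone hold for every E from 0 to 500 and fail for every E above 500. So the claim that they agree only at exactly 500 depends on treating the rationale as a third rule.

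**What it takes for the ceiling to bind.** The window in section 4 is 851 days, or 28 months: 365 days before January 2023 and 486 from then on. The threshold is 500 / 28 = 17.9 eligible patients a month. Each must have had a carotid endarterectomy with this patch and a postoperative ultrasound. Covering all campuses pushes the count up. The ultrasound requirement and the expected screen failures push it down. The protocol gives no figure that settles it.

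**What happens if it binds.** This needs assumptions that are not in the protocol: 800 eligible, uniform volume, a 0.3 SD difference in a duplex measure, and a two-sided 5% t-test.

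- Eligible by period: 800 × 365/851 = 343 old and 457 new.
- Proportional draw of 500: 500 × 365/851 = 214 old and 286 new.
- Date order: the ceiling is reached on day 851 × 500/800 = 532, about 16 June 2023. This keeps 343 old and 500 − 343 = 157 new.
- Reverse date order: all 457 new and 500 − 457 = 43 old.

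In the normal approximation, power is Φ(0.3 × √(n₁n₂/(n₁+n₂)) − 1.96):

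| Fill | Old / new | √(n₁n₂/500) | Power (t-test) |
|---|---|---|---|
| Proportional | 214 / 286 | 11.06 | 91.2% |
| Date order | 343 / 157 | 10.38 | 87.4% |
| Reverse order | 43 / 457 | 6.27 | 46.7% |

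Date order costs 91.2 − 87.4 = 3.8 percentage points. Only reverse filling does serious damage, and nothing in the protocol suggests it.

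**What happens below the ceiling.** With the same test and uniform volume, power for 0.3 SD is 84.2% at 400 patients, 72.7% at 300 and 55.2% at 200. These values depend on how many patients exist. Since everyone eligible is included anyway, no rewording of the size sentences moves them.

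**The case for a change.** The strongest case for a change is that the ceiling and the inclusion rule do conflict above 500, and the protocol cannot exclude that count. Selection would then be undefined in a comparison split by date. The outcomes are already on file, and section 16 names the patch's manufacturer as funder, which is a reason to fix selection beforehand though no evidence of bias. It can also be said that the ceiling may count charts reviewed rather than patients enrolled, and that 500 is not robust for rare complications: at assumed rates of 2% and 4%, power with 214 and 286 patients is 23.4%.

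Part of this stands. The conflict above 500 is real in logic, and if it arose someone would have to decide which sentence governs. The rest carries less weight. Identifying patients from records is how any chart review works, and including everyone eligible points away from choice by outcome. If 500 counts charts, the threshold is reached in charts instead of eligible patients, but the protocol gives no count of those either. As for rare events, the sentence speaks of a baseline for studying differences and trends. It makes no power claim for any complication, and narrowing the adjective would not add a patient.

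**Conclusion.** The concern does not call for a change. The natural reading is that everyone eligible in the window is included and 500 is an upper bound. On that reading the plan is coherent for any eligible count up to 500, and following it as written gives the complete cohort. If fewer qualify, the sentence about 500 describes the ceiling and not the achieved size; that is a loose justification, not a clash of rules.

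The only true conflict needs more than 500 eligible patients, above about 17.9 a month for 28 months, and the protocol does not show that this happens. In the assumed case of 800 eligible, the loss from plain date-order filling is about 4 percentage points of power. An overflow rule is operational detail that could also stand in an analysis plan not available here.

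The conclusion rests on the eligible count not exceeding 500, or on any excess being handled without regard to outcome. A screening count above 500 would make the conflict real, and the choice between the two sentences would then have to be settled before outcomes are abstracted.

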**Data to be collected:**

- Age at surgery, sex, race
- Preoperative risk factors: HTN, DM, TIA, CAD, HLD, previous strokes, previous thromboembolic events, previous surgeries
- Intraoperative data: Type of patch material used, intraoperative complications (if any), MAP, Heart rate, Medications given, Estimated blood loss, Intraoperative antibiotics given, Intraoperative antiplatelet/anticoagulation medication given
- Postoperative outcomes: Stroke/TIA, Postop ICU time, mortality (up to 30 days)
- Follow up neurological evaluation, any symptoms reported by the patient
- Imaging: MRI/CT, MRA, CTA, TCD, vascular duplex ultrasound

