**The objectives of this study include:**

*Ultrasound evaluation of Baxter VASCU-GUARD vascular patches:*

Retrospective review of ultrasound recordings and ultrasound reports at one-month, 3-months, 6-months and 1-year follow-up after endarterectomy – if available, to evaluate patch patency, morphology, integrity, complications, and blood flow dynamics.

*Complications assessment:*

Analyze complications linked with Baxter Vascular Patches (VASCU-GUARD), including but not limited to thrombosis, stroke, dissection, restenosis, infection, fluid collection, pseudoaneurysm formation, fraying or irregularities in patch material.

*Correlation with Clinical Outcomes:*

Recognize correlations between ultrasound findings and clinical outcomes. This correlation will complement the understanding of how ultrasound monitoring can predict and influence patient prognosis.

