## **8. Data Privacy / Confidentiality**

Required for all protocol types including Sponsored trials. Provide local information.

The data will be abstracted from Houston Methodist Hospital electronic medical records by the PI and trained members of his research staff. The required information will be transferred from electronic medical records by the research staff to the study specific data collection forms.

Study data will be registered into an electronic, password protected database located on the TMHS server accessible only by the research team, applicable regulatory personnel and authorities.

Documents requiring an investigator's signature, should any be created, will be promptly signed, and dated in real-time. In accordance with departmental policies, research-specific documents will be retained on-site for 6 years post-study closure.

No images, video recordings, or photographs of patients will be requested for this study. Study will remain minimal risk with provisions to limit the risk of loss of confidentiality, outlined in section 17. Minimal PHI identifiers will be utilized to build the cohort. Identifiers will not be utilized for cohort analysis. Sufficient security and data privacy measures will be implemented in terms of data collection, processing, storing, and maintaining the database as per the institutional policies and the regulations of the Health Insurance Portability and Accountability Act of 1996 (HIPAA). Study site/investigators will not disclose any proprietary information or confidential data.

As applicable, the IRB, FDA, or other relevant health authorities will have the right to review study data at any point in time.

Identifier (or parts of)	Recorded	Disclosed	Comment
Names	Yes	No	This information will be gathered for the chart review and will not be provided or shared with anyone not part of the research team or outside of the institution. Only for the purpose for screening patients of inclusion in cohort.
All elements of dates (except year) for dates directly related to an individual, including birth date, admission date, discharge date, date of death; and all	Yes	No	This information will be gathered for the chart review and will not be provided or shared with anyone not part of the research team or outside

**PROTOCOL TITLE: *Ultrasound Evaluation for Baxter VASCU-GUARD Vascular Patches Post-Endarterectomy and Complications Assessment***

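### The listed data give no event date or last-contact date for clinical outcomes found without a scan, so time at risk after the last ultrasound cannot be computed, and the calendar split makes unequal follow-up by packaging group likely

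*Protocol*

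**What the plan says.** **Outcomes.** The complications objective in Protocol Section 2 covers complications "including but not limited to thrombosis, stroke, dissection, restenosis, infection, fluid collection", among others. Stroke and infection can occur, and be recorded in a chart, without an ultrasound. In Section 4, the list of data to be collected has "Postoperative outcomes: Stroke/TIA, Postop ICU time, mortality (up to 30 days") and then "Follow up neurological evaluation, any symptoms reported by the patient". Thirty days is the only window given, and it follows mortality. The neurological evaluation and the symptoms carry no date or visit window.

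**Dates.** In Section 4, Medical Records Review, the dates named are "date of operation/procedure, discharge date", in a list that ends with an open et cetera. The identifier table in Section 8 covers further dates, "including birth date, admission date, discharge date, date of death; and all", but the comment beside them reads "Only for the purpose for screening patients of inclusion in cohort". The text of the same section adds "Identifiers will not be utilized for cohort analysis".

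**Follow-up.** The Section 2 review schedule of 1, 3, 6 and 12 months applies to ultrasound, where available. Section 10 requires a follow-up ultrasound but sets no minimum time for it.

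**Comparison and window.** The groups are old packaging (before January 2023) and new packaging (after January 2023). Section 4 gives the data period as 1 January 2022 to 30 April 2024.

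**The concern.** A chart review finds a late stroke or infection only if the patient comes back to a source that is searched. To turn such events into a risk, one must know how long each chart would have shown an event had there been one. The listed items do not give that for clinical outcomes. After the last scan, a patient who was seen and well looks the same as a patient who was not seen.

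Two consequences should be kept apart. The absolute complication rate is understated whenever silence is read as no event, in either group. The comparison of packaging is distorted only if the two groups were in contact for different lengths of time. Because the groups are successive calendar periods inside one closed data window, equal length of contact cannot be taken for granted. An analysis plan can choose a censored analysis, but it needs a censoring date to have been abstracted.

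**Working it through.** The protocol states no event rate, loss rate or length of follow-up, so there is no figure to reproduce. The risks, loss shares and hazard shapes below are assumptions. The calendar dates are the protocol's.

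**1. Can time at risk be built from the listed items?** It needs a start and an end. The start is the operation date, which is listed. The end is the event date or the last date on which the patient was known to be event-free. For ultrasound findings, the scan time point supplies it. For stroke/TIA, infection and symptoms, no item does. The death date in Section 8 would supply an end for deaths, but it is marked for screening only.

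**2. What does missed follow-up do?** Let p be the true 1-year risk in both groups, and L the share of events that fall after the chart goes silent and are read as no event. Observed risk = p × (1 − L). With p = 5%:

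| L old | L new | Observed old | Observed new | Ratio new/old |
|---|---|---|---|---|
| 20% | 20% | 4.0% | 4.0% | 1.00 |
| 40% | 40% | 3.0% | 3.0% | 1.00 |
| 20% | 40% | 4.0% | 3.0% | 0.75 |
| 40% | 20% | 3.0% | 4.0% | 1.33 |

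Equal loss lowers both rates and leaves the ratio at 1. Unequal loss moves the ratio in favour of the group with the shorter contact. The ratios do not depend on p.

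**3. Do the protocol's dates make contact unequal?** Take the split at 1 January 2023, even accrual, and 30 April 2024 as the end of both surgery and follow-up. Old-packaging surgeries span 365 days and new-packaging surgeries 485 days.

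- The last old-packaging patient still has about 485 days to the cutoff, so all can reach 1 year.
- New-packaging patients who can reach 1 year: (485 − 365)/485 = 120/485 = 24.7%.
- New-packaging patients who can reach 6 months: (485 − 182)/485 = 62.5%; 3 months: (485 − 91)/485 = 81.2%; 1 month: (485 − 30)/485 = 93.8%.

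**4. Size from the cutoff alone, with no other loss.** With a constant hazard h = −ln(1 − p)/365, the observed new-group risk is the mean of 1 − exp(−h × min(365, t)) over t from 0 to 485 days. The old group shows p.

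| p | New group shows | Ratio |
|---|---|---|
| 3% | 1.9% | 0.63 |
| 5% | 3.1% | 0.63 |
| 10% | 6.3% | 0.63 |

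A hand check with events spread evenly over the year: (365/2 + 120)/485 = 302.5/485 = 0.62.

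**5. How sensitive is this?**

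- *Early events.* Suppose half of the year's events fall in the first 30 days and the rest evenly over the other 335. The share of events seen in the new group is (30 × 0.25 + 335 × 0.75 + 120)/485 = 378.75/485 = 0.78.
- *Scan requirement.* Patients operated on just before the cutoff may have no scan and so be ineligible. If those with under 30 days are dropped, the even-spread figure becomes ((365² − 30²)/730 + 120)/455 = 301.27/455 = 0.66, and the early-event figure (335 × 0.75 + 120)/455 = 371.25/455 = 0.82.

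The bias shrinks under these variations but keeps its direction.

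**The case against.** **The scans already date contact.** Every included patient has at least one follow-up ultrasound, and scans are reviewed by time point. A reader might infer that a patient scanned once at 1 month cannot be told from one seen at 1 year. That goes too far: the last scan gives each patient a known minimum contact, and a recorded neurological evaluation adds some evidence. This stands, and it confines the gap to the time after the last scan. It does not close the gap for outcomes that need no scan.

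**No coding rule is stated.** Nothing in the protocol says that a silent chart counts as event-free or that crude proportions will be used, and the handling of censoring may sit in an analysis plan that is not shown. This also stands. Reading silence as no event is a likely default, not a stated rule. The point here concerns which data are abstracted, and an analysis plan cannot supply those on its own.

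**The lists are open.** The operative list ends in an et cetera, so further items may be abstracted. Age at surgery and the scan time points are themselves derived from dates, so Section 8 may not be meant to bar intervals. As written, though, no last-contact item is named and the stated use of recorded dates is screening.

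**The horizon may be short.** If the 30-day window covers the whole outcome line, stroke/TIA on that line is little affected by later silence. The wording is ambiguous. Infection and later symptoms would still have no horizon.

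**The size is assumed.** This is true of every risk and loss share above. Only the calendar dates come from the protocol, and step 3 also assumes that the window closes follow-up. If follow-up was read beyond 30 April 2024, that source of imbalance shrinks or vanishes.

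**Conclusion.** The gap is real but limited. For clinical outcomes found without a scan, the listed data do not allow time at risk after the last ultrasound to be computed. Where silence is read as no event, absolute complication rates are understated in both groups. The packaging comparison is biased only if length of contact differs.

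The protocol's dates make a difference likely, in the direction that favours the new packaging. If the window closes both surgery and follow-up and accrual is even, all old-packaging but only about 25% of new-packaging patients can reach 1 year. The false ratio is then about 0.63 under a constant hazard, and about 0.78 if half the events fall in the first month. Mortality has a fixed 30-day window and is much less exposed.

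Two stronger readings are not supported. A reader might infer that loss to follow-up favours the patch in the comparison. Both groups received the same patch, and equal loss leaves the ratio at 1. A reader might also infer that the gap can never be repaired. Names and record numbers are recorded, so the charts can be reopened while that linkage is kept, at the cost of a second pass. The change should be made, but it does not invalidate the study.

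**What to change.** 1. In Section 4, data to be collected, add two fields: days from surgery to last documented clinical contact or death, whichever is first; and days from surgery to first stroke/TIA or other clinical complication.
2. In Section 8, state that intervals derived from recorded dates may be used in analysis. The dates themselves need not leave the screening file.
3. Compare these outcomes by packaging group with censoring at last contact up to one common horizon, or over a fixed window that both groups can complete.
4. Say whether 30 April 2024 closes surgery, follow-up or both, and whether the 30-day window applies to stroke/TIA.
5. Report length of contact by group beside the event results.

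The cost is a few minutes of abstraction per chart, for at most 500 charts that will be open in any case, and a standard time-to-event routine in STATA. One limitation should be stated: censoring at last contact assumes that contact is unrelated to outcome. Patients may return because they have symptoms, so that assumption can fail.
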